5.5 Strategies for Recruitment and Retention

Patients may be prescreened (through medical records/phone script) and will be contacted and informed about the study ahead of time, at least 1 day before their appointment. We will try our best to contact patients and inform them about the study ahead of time, but sometimes it may not be possible. The Endodontics clinic is a referral based clinic, sometimes we see new external referrals or emergency patients. We don't have any direct contact with those patient ahead of time, and sometimes emergency patients would show up without prior appointments. Thus, patient may be included even if they haven't been contacted prior.

Patients presenting to the Department of Endodontics, School of Dental Medicine (PDM), University of Pennsylvania for evaluation and routine endodontic treatment of infected, necrotic teeth with chronic apical periodontitis will be asked to take part in the study if they appear to meet the inclusion criteria specified above. Patients will be asked if they were interested to participate in this investigation after a clinical diagnosis matching is confirmed and the patient/tooth meets the inclusion criteria specified above. Initial clinical diagnosis will be made by a postgraduate resident and verified by the supervising faculty. The PI, a full-time faculty, and the co-investigator, endodontic resident, will be informed about a potential study participant, verify the diagnosis and ask for participation (including consent and alternatives). Any recruitment materials that are developed will be submitted to the IRB for approval prior to use. No non-registered PDM patients will be asked to participate in the study.

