6.3 Measures to Minimize Bias: Randomization and Blinding

Simple randomization by generating simple allocation sequence, allocation concealment, and implementation of the random allocation sequence upon enrollment.

As this is part of a procedure, the investigator and study participant cannot be blinded to the treatment. To minimize bias, the investigator will provide the same information regarding reporting pain to all study participants.

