Treatment success determined clinically and radiographically: Radiographically, Following periapical (PAI) index by Órstavík², description of radiographic findings: 1. Normal periapical structures. 2. Small changes in the bone structure. 3. Change in the bone structure with mineral loss. 4. Periodontitis with a well-defined radiolucent area. 5. Severe periodontitis with exacerbating features. Success is defined as either complete (radiographic resolution of a periapical lesion - the radiographic sign of inflammatory processes surrounding a root tip) or incomplete healing (scar tissue formation) and failure includes uncertain healing (radiographic reduction of a periapical lesion or same lesion size) or unsatisfactory healing (increase in lesion size) as determined on the radiograph. Clinically, success is defined by the absence of pain, swelling, percussion sensitivity or sinus tracts. Clinical failure is defined as the persistent presence of any of the symptoms mentioned above. Treatment success/failure measured at the standard of care 6 month, 1 year and 2 year follow up (± 7 days) post root canal filling.

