8.2 Safety and Other Assessments

The resident performing the endodontic treatment will evaluate and treatment plan the case as routinely performed through a clinical and radiographic examination of the involved teeth. At least one periapical radiograph of the involved tooth will be obtained during the consultation as routine protocol requires for every root canal treatment. In order to be eligible to participate in this study, an individual must meet all of the previously mentioned criteria (check section 5.1 and 5.2). On the day of procedure, the resident will conduct and complete the root canal treatment as standard protocol requires, including medical history review/update, clinical assessment, vital signs (blood pressure). Participants, providers and observers will wear appropriate laser protection eyewear (OD 3 or greater) whenever the laser is in use.

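### No masked reading of the follow-up radiographs is planned, although the reason given in 6.3 for not blinding does not apply to a film reader

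*Combined protocol and SAP*

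**What the plan says.** Section 6.3 is the only text on blinding to treatment. It names two roles, in the words "the investigator and study participant cannot be blinded to the treatment", and gives one reason: "As this is part of a procedure". Beyond randomization and allocation concealment, its one measure against bias is that "the investigator will provide the same information regarding reporting pain to all study participants". It does not mention outcome assessors.

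Section 8.1 lists the five periapical index descriptions and then defines radiographic success as complete healing or incomplete healing with scar. By contrast, "failure includes uncertain healing (radiographic reduction of a periapical lesion or same lesion size"), and so does an enlarging lesion, all "as determined on the radiograph". The timing is given as "Treatment success/failure measured at the standard of care 6 month, 1 year and 2 year follow up". The same definition appears in 1.1, 3, 9.1 and 9.4.3. None of these sections says who reads the films, how many readers there are, or whether they know the arm.

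The only person linked to a radiographic examination is the operator, at consultation: "The resident performing the endodontic treatment will evaluate and treatment plan the case as routinely performed through a clinical and radiographic examination" (8.2, repeated in 9.4.4).

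**The concern.** The boundary between success and failure falls where the reading is least objective. A smaller but persistent radiolucency can be called scar, which is a success, or reduction, which is a failure. The periapical index is described, but no cut-off on it defines success. A reader who knows the arm could resolve borderline films differently by arm without intending to.

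The stake is the trial's only long-term efficacy outcome. Sections 1.1, 2.1 and 3 give better root canal treatment success as the eventual aim. A difference produced by reading would look like a treatment effect, and a true difference could be masked in the same way.

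**Working it through.** **Step 1. Does the stated reason reach the film reader?**

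| Role | Contact with the visit 1 procedure | Covered by the reason in 6.3? |
|---|---|---|
| Operator | Performs it | Yes |
| Participant | Undergoes it | Yes |
| Reader of films at 6 months, 1 year, 2 years | None needed | No; 6.3 is silent |

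**Step 2. Could the film reveal the arm?** Under 4.1 the arms differ only in the canal step before the second sample: hypochlorite between files, or saline between files followed by laser. Ultrasonic hypochlorite irrigation, further enlargement, calcium hydroxide and root filling are then common to both. Nothing described leaves an arm-specific mark on a follow-up film.

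**Step 3. Are the means in place?** The schedule in 12.1 already includes imaging at all three follow-up visits. Section 10.1.3 already gives research data a unique study number.

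**Step 4. How large could the effect be?** The plan gives no expected success rate, test or power for this endpoint, so there is no figure of its own to reproduce. The following is an illustration.

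Inputs:
- 38 per arm enrolled (9.2). With the 30% attrition assumed there, 38 × 0.70 = 26.6, about 27 per arm.
- Two-sided 5% level (9.1, 9.2).
- Assumed: true success 70% in both arms. Section 2.2 cites 68% and 94% success after positive and negative cultures, so 70% is near the lower figure.
- Assumed: knowledge of the arm moves 5, 10, 15 or 20 points of one arm from failure to success. As a share of that arm's 30 points of failure, this is 5/30 = 1/6, 10/30 = 1/3, 15/30 = 1/2 and 20/30 = 2/3.

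Formula: P(reject) = Σ over a, b of Bin(a; n, 0.70 + shift) × Bin(b; n, 0.70) × 1[test of a/n versus b/n has p ≤ 0.05], summed exactly.

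| Shift | Chi-square, n = 38 | Fisher, n = 38 | Chi-square, n = 27 | Fisher, n = 27 |
|---|---|---|---|---|
| 0 | 5.2% | 3.0% | 5.4% | 2.5% |
| 5 points | 8.0% | 4.9% | 7.6% | 3.6% |
| 10 points | 17.3% | 11.8% | 14.6% | 7.5% |
| 15 points | 34.9% | 26.3% | 27.9% | 15.9% |
| 20 points | 60.7% | 50.4% | 48.7% | 31.2% |

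The chi-square is uncorrected. Fisher's exact test is shown because it is the only categorical test the plan names, though 9.4.5 names it for baseline data.

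**Step 5. Sensitivity to the assumed success rate.** Let p be true success in both arms and u the share of laser-arm failures upgraded. Apparent laser success is p + u(1 − p), so the false difference is u(1 − p). The chance of a significant result favouring laser at 38 per arm (normal approximation, nominal 2.5% in that direction) is:

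| p | u = 10% | u = 25% | u = 50% |
|---|---|---|---|
| 68% | 3.2 points, 4.9% | 8 points, 11.7% | 16 points, 37.0% |
| 80% | 2 points, 4.1% | 5 points, 8.2% | 10 points, 22.8% |
| 94% | 0.6 points, 3.2% | 1.5 points, 4.8% | 3 points, 9.1% |

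The risk depends on how many failures there are to reclassify. If nearly all teeth heal, it is small.

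**The case against.** The best reply is that the plan is silent, not wrong, and that the endpoint is secondary with no stated test or power. Several stronger readings are tempting, and the documents do not support them.

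- A reader might infer that 6.3 rules out blinding for the whole trial. It names only the investigator and the participant.
- A reader might infer that the treating resident scores the follow-up films with the arm known. Section 8.2 ties the resident to the consultation examination only, and the follow-up reader is not identified.
- A reader might infer that supervising faculty are the planned readers, because 5.5 says "Initial clinical diagnosis will be made by a postgraduate resident and verified by the supervising faculty". That concerns diagnosis at recruitment, not outcome reading.
- A reader might infer that a reading bias could never be detected later. Films are taken at each follow-up visit and 10.1.8.2 requires study documents to be retained, so if the images are kept a masked re-reading could test for bias and its direction. A re-reading decided on after the results are known is, however, less convincing than one planned in advance.
- A reader might infer that masking is free. It takes some file handling and reading time.

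The size of the effect is also open to challenge. A 20-point shift reclassifies two-thirds of one arm's failures, all in one direction. Failures include unchanged and enlarged lesions, which are hard to call scar. Fisher's test gives lower rates than chi-square. These objections limit the figures. They do not answer the central point: a bias-prone reading is left open when the stated obstacle to masking does not apply to it.

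**Conclusion.** The concern holds for the radiographic part of the success endpoint. No masked reading is planned, the reason in 6.3 does not extend to a film reader, and the scar-versus-reduction call is a judgement. A change to the plan is warranted.

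The size is illustrative only. With 70% true success in both arms and a 10 to 20 point shift in one direction, the false-positive rate at 38 per arm is about 17% to 61% (uncorrected chi-square) or 12% to 50% (Fisher). At 5 points it is about 8% or 5%. The success rate, the shifts and the choice of test are all assumptions, so these figures should not be read as the error rate expected in this trial.

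Nor do they bear on the chairside clinical success criteria, which coding films does not mask, or on the primary CFU comparison. Sample size, alpha and power are unchanged.

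**What to change.** In 6.3, keep the statement about investigator and participant and add that readers of follow-up radiographs will be masked to arm. In 8.1, state that:

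- films from the 6-month, 1-year and 2-year visits are exported under the study ID, with arm and operator removed;
- they are scored in random order;
- the readers are existing department investigators or faculty who neither treated nor supervised that tooth and are unaware of the arm.

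The cost is modest file handling and reading time. No extra visit, imaging, treatment change or participant is needed. The documents do not show how many suitable readers the department has, so the sponsor should confirm that enough are available.

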6.4 Study Intervention Compliance

The study intervention will occur during a routine endodontic procedure. Administration of the study intervention will be done by qualified personnel and recorded in the case report forms.

6.5 Concomitant Therapy

For this protocol, a prescription medication is defined as a medication that can be prescribed only by a properly authorized/licensed clinician. Medications to be reported in the Case Report Form (CRF) are concomitant prescription medications, over-the-counter medications and supplements.

6.5.1 Rescue Medicine

All participants will be provided with the Post Endodontic Treatment Instructions form (*attachment 6*). This form will include those information regarding rescue medicine:

Take 1000-mg acetaminophen as needed. (Tylenol; 2 tablets of 500mg as needed).

If acetaminophen was consumed, the patients will be asked to record the dose and time on the survey.

7 STUDY INTERVENTION DISCONTINUATION AND PARTICIPANT DISCONTINUATION/WITHDRAWAL

7.1 Discontinuation of Study Intervention

If the subject is discontinued from the study intervention, they will be withdrawn from the study. The reason for withdrawal will be recorded in the case report forms.

7.2 Participant Discontinuation/Withdrawal from the Study

Participants are free to withdraw from participation in the study at any time upon request.

An investigator may discontinue or withdraw a participant from the study for the following reasons:

- Significant non-compliance to attend scheduled visits
- If any clinical adverse event (AE), laboratory abnormality, or other medical condition or situation occurs such that continued participation in the study would not be in the best interest of the participant
- Disease progression which requires discontinuation of the study
- If the participant meets an exclusion criterion (either newly developed or not previously recognized) that precludes further study participation

The reason for participant discontinuation or withdrawal from the study will be recorded on the Case Report Form (CRF). Subjects who sign the informed consent form and are randomized but do not receive the treatment may be replaced. Subjects who sign the informed consent form and are randomized and receive the treatment, and subsequently withdraw, or are withdrawn or discontinued from the study, will not be replaced.

7.3 Lost To Follow-Up

A participant will be considered lost to follow-up if he or she fails to return for 1 scheduled visit and is unable to be contacted by the study site staff.

The following actions must be taken if a participant fails to return to the clinic for a required study visit:

- The site will attempt to contact the participant and reschedule the missed visit (1 month) and counsel the participant on the importance of maintaining the assigned visit schedule and ascertain if the participant wishes to and/or should continue in the study.
- Before a participant is deemed lost to follow-up, the investigator or designee will make every effort to regain contact with the participant (where possible, 3 telephone calls and, if necessary, a certified letter to the participant's last known mailing address or local equivalent methods). These contact attempts should be documented in the participant's medical record or study file.
- Should the participant continue to be unreachable, he or she will be considered to have withdrawn from the study with a primary reason of lost to follow-up.

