Study Duration:	The projected time frame for this research project is from June 2023 to June 2027. Enrollment is from June 2023 to June 2025. Followed by 2 years for the last follow up, which is the date of the second visit for the last subject enrolled +2 years (± 7 days). The recruitment, treatment and analysis of 76 subjects with teeth matching the inclusion criteria can be reasonably achieved within these 4 years.
Participant Duration:	The subjects will participate in the study for 2 years. This is the standard of care timeline for routine root canal therapy with 6 months, 1 year, and 2 year follow up.

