12 APPENDIX

12.1 Schedule of Activities (SoA)

Procedures	Pre-Screening Up to Day 0	Enrollment/Baseline Visit 1, Day 0	Study Visit 2 Day 7 +/-3 days	Study Visit 3 6 months +/-7 days	Study Visit 4 1 year +/-7 days	Study Visit 5 2 years +/-7 days
Prescreening (medical records, phone script)	X					
Study informed consent		X				
Demographics		X				
Medical history review/update		X	X	X	X	X
Clinical assessment		X	X	X	X	X
Vital signs (Blood pressure)		X	X	X	X	X
Randomization		X				
Administer study intervention		X				
Sample collection		X				
Pain Assessments (pre-op, and 4, 24, and 48 hours post-op)		X				
Adverse event review and evaluation		X	X	X	X	X
Radiologic/Imaging assessment		X	X	X	X	X
Completion of the study						X

END OF DOCUMENT

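### Section 7.3 treats one uncontactable missed visit as withdrawal, with no route to use later standard-of-care recall outcomes, and its 1-month rescheduling note is not reconciled with the ±7-day windows

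*Combined protocol and SAP*

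**What the plan says.** Section 7.3 sets two conditions for loss to follow-up: the participant "fails to return for 1 scheduled visit and is unable to be contacted by the study site staff". Before that status is assigned, the site must make every effort to regain contact, where possible by "3 telephone calls and, if necessary, a certified letter to the participant's last known mailing address or local equivalent methods", and must document the attempts. If these fail, "he or she will be considered to have withdrawn from the study with a primary reason of lost to follow-up". A participant who is reached is rescheduled and may continue.

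Section 7.2 treats missed visits differently: the investigator may withdraw a participant for significant non-attendance, which is discretionary. It also says that treated participants who later withdraw are not replaced.

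On timing, the first action in 7.3 is this: "The site will attempt to contact the participant and reschedule the missed visit (1 month", with the bracket closing there and no explanation of what the month measures. The schedule in 12.1 gives "Study Visit 3 6 months +/-7 days" and the same tolerance at 1 and 2 years. The ±7 days is also written into the treatment-success endpoint in 1.1, 3, 8.1, 9.1 and 9.4.3.

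On the 6-month, 1-year and 2-year follow-up, the Synopsis says: "This is the standard of care timeline for routine root canal therapy".

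**The concern.** The rule merges two different events: being unreachable at one point in time, and leaving the trial. A patient who misses the 6-month recall and cannot be traced may still come back to the same department at 1 or 2 years, be examined and have a radiograph. That patient would already be recorded as withdrawn, and nothing says whether the outcome is trial data.

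Two things are at stake. The first is avoidable missing data on the clinical and radiographic success endpoint, for which the two-year follow-up exists, and on the adverse event review scheduled at the same visits. If attendance depends on symptoms, which is plausible but not addressed in the documents, the loss could also be informative. The second is that the choice to include or exclude a returning patient, or a late visit, would be made after the outcome is known, in a trial where 6.3 says the investigator is not blinded.

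**Working it through.** **What happens to a returning participant.** Section 7.3 ends at withdrawn status. Section 7.2 covers reasons for withdrawal and replacement, not data collected afterwards. Section 9.3 describes the eligible patients and defines no analysis set. Section 9.4.3 repeats the endpoint definitions and gives no missing-data method. So no text excludes later outcomes, and no text admits them.

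**Endpoints exposed.** Samples S0 to S3 are all taken at Visit 1 (1.2, 12.1), before any recall, so the CFU comparison is untouched. Treatment success at 6 months, 1 year and 2 years is exposed, as is adverse event review at those visits.

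**The plan's own figure.** With effect size 0.8, two-sided alpha 0.05 and 80% power (9.2), a two-sample t-test needs 26 per group (power 80.7%). Inflating for 30% attrition, 26 / 0.70 = 37.1, rounded up to 38 per group, or 76. The stated numbers reproduce and are not in dispute. The 30% is an allowance in the CFU calculation, not a recall-loss rate.

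**Illustration of size.** The documents give no missed-visit rate. Assume that each of the three recalls is missed independently with probability p, that every miss is uncontactable, that withdrawal is permanent under the rule, and that without the rule those people attend at 2 years at the normal rate. Then the fraction with a 2-year outcome is (1 − p)³ under the rule and 1 − p if later attendance counts. Per arm of 38:

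| p (assumed) | Under the rule | Later recalls used | Gap |
|---|---|---|---|
| 5% | 0.857 × 38 = 32.6 | 0.950 × 38 = 36.1 | 3.5 |
| 11.2% | 0.700 × 38 = 26.6 | 0.888 × 38 = 33.7 | 7.1 |
| 15% | 0.614 × 38 = 23.3 | 0.850 × 38 = 32.3 | 9.0 |

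The 11.2% is solved backwards from the 30%: 1 − 0.70^(1/3) = 0.112. Its agreement with the plan's attrition figure is therefore by construction and is not evidence for it.

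**Milder assumptions, still at p = 11.2%.** The number recoverable per arm is the fraction lost at the first two recalls, times the fraction who return at 2 years, times 38.

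- Half of misses uncontactable (0.056 per visit), half return: (1 − 0.944²) × 0.5 × 38 = 0.109 × 19 = 2.1.
- Half uncontactable, a quarter return: 0.109 × 0.25 × 38 = 1.0.
- All uncontactable, half return: (1 − 0.888²) × 0.5 × 38 = 0.211 × 19 = 4.0.

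**Window check.** Take a month as about 30 days from the scheduled date, and read the 1 month as a rescheduling allowance. A rescheduled recall can then fall 30 − 7 = 23 days past its window. At Visit 2, where 12.1 allows ±3 days, it is 30 − 3 = 27 days. No text says whether such a visit meets the endpoint definition.

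**The case against.** The strongest reply is that 7.3 is a safeguarded rule and the rest is silence. A missed visit alone triggers nothing: the site must try to contact and reschedule the participant, and anyone reached can continue. That stands, and it limits the rule to participants who are truly unreachable. It does not make the status reversible.

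A reader might infer that the plan orders later outcomes to be thrown away. The documents do not support that: no passage says data after loss to follow-up are discarded, and no analysis set drops withdrawn participants. The point is the absence of a route to use them.

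A reader might also infer that the 1 month contradicts the ±7 days. That is too strong. A target window and a make-up period can coexist, and the bracketed month could instead be the time allowed for making contact. The two are unreconciled, and because ±7 days is part of the endpoint definition as well as the schedule, the ambiguity matters for the analysis.

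Finally, 27 versus 34 per arm should not be read as an expected loss. Section 5.5 describes a referral clinic that also sees external referrals and emergency patients, so people who cannot be traced may not return at the usual rate. Section 9.4.3 names no test for treatment success, so the figures correspond to no planned power. Both criticisms stand.

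**Conclusion.** The concern holds as a shortcoming in the follow-up rules that should be corrected. As written, 7.3 turns one uncontactable miss into withdrawal with no way back, although later outcomes may be obtainable from standard-of-care recalls. The possible harm is confined to the secondary treatment-success endpoint and later adverse event follow-up.

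The amount lost cannot be stated from the documents. At an assumed 11.2% miss rate, about 7 per arm is an upper bound, provided that those lost would attend at 2 years no more often than everyone else. About 1 to 4 per arm is recoverable under the milder assumptions shown. No difference between arms has been shown.

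The timing point rests on reading the 1 month as a rescheduling allowance. On that reading a recall can fall about 23 days outside its window with no rule for its use; on any other reading the text still needs explaining.

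**What to change.** - In 7.3, record an earlier uncontactable miss as a missed visit. Accept any later recall as study data unless the participant has withdrawn consent. Assign final lost-to-follow-up status only when the 2-year visit has been missed and the contact attempts have failed.
- Say in 7.3 what the 1 month refers to, and reconcile it with the ±7-day windows in the endpoint definition and 12.1, and with the ±3 days at Visit 2.
- In 9.4.3, state that out-of-window outcomes are kept and analysed with their actual date.

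The cost is protocol wording. The recalls are already standard of care and already in the schedule, so no visit or radiograph is added. The downside is that some outcomes will be assessed at less uniform times, which is why the actual date has to enter the analysis.
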